4.4 END OF STUDY DEFINITION

A participant is considered to have completed the study if he/she has completed all phases of the study including a 2 to 4 day follow-up period.

The end of the study is defined as the date of the "last patient last visit" planned with the protocol, including the follow-up visit.

5 STUDY POPULATION

Prospective approval of protocol deviations to recruitment and enrollment criteria, also known as protocol waivers or exemptions, is not permitted.

5.1 INCLUSION CRITERIA

Participants are eligible to be included in the study only if all of the following criteria apply:

Age

I 01. Participant must be 18 to 70 years of age inclusive, at the time of signing the informed consent.

Type of participant and disease characteristics

- I 02. Participants with T1DM.
- I 03. Participants treated with multiple daily injections (MDI) using basal insulin analog once daily and rapid acting insulin analogs for at least one year.
- I 04. HbA1c \geq 7% (48 mmol/mol) and \leq 10% (86 mmol/mol) at screening.

Sex

- I 05. Male or Female
 - a) Female participants: A female participant is eligible to participate if she is not pregnant (see Appendix 4 [Section 10.4]), not breastfeeding, and at least one of the following conditions applies:
 - Not a woman of childbearing potential (WOCBP) as defined in Appendix 4 (Section 10.4),

OR

b) A WOCBP who agrees to follow the contraceptive guidance in Appendix 4 (Section 10.4) during the intervention period.

Informed Consent

I 06. Capable of giving signed informed consent as described in Appendix 1 (Section 10.1.2) which includes compliance with the requirements and restrictions listed in the informed consent form (ICF) and in this protocol.

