At Week 12, the following endpoints will be assessed:

- Glucose total CV
- Glucose within-day and between-day CV

Other secondary endpoints:

- Change from baseline to Week 12 in HbA1c
- Change from baseline to Week 12 in central lab FPG
- Percent time and mean hours per day with glucose<70mg/dL (on all time and during the night [00:00 to 05:59])
- Percent time and mean hours per day with glucose>180mg/dL

To evaluate the safety of insulin glargine 300 U/mL in comparison to insulin degludec 100 U/mL

Number of participants with adverse events (see Section 8.3)

Number of participants with at least one hypoglycemic event from baseline to Week 12

Number of hypoglycemic events per participant year from baseline to Week 12

Overall design:

This is a multicenter, randomized, active-controlled, parallel-group, 12-week open-label study to compare the efficacy of Toujeo with Tresiba using 20-day CGM glucose profiles at Week 12. The CGM during study period will be blinded to both the Investigators and patients.

Study population will consist of participants with type 1 diabetes mellitus (T1DM), treated with multiple daily injections (MDI) using basal insulin once daily and rapid acting insulin analogs for at least one year, and having HbA1c \geq 7% and \leq 10% at screening (see full list of inclusion and exclusion criteria in Section 5).

Number of participants:

Approximately 338 patients will be randomly assigned to study intervention for an estimated total of 131 evaluable participants per intervention group (with the assumption of a non-evaluability rate of 22%).

Intervention groups and duration:

The study is planned to randomize 338 patients in 2 parallel treatment groups:

- Toujeo group, n=169 patients.
- Tresiba group, n=169 patients.

The duration of the study per patient will be around 18 weeks (1 or 2 weeks of screening followed by a 4-week run-in period, a 12-week treatment period and a 2 to 4 days follow-up period).

Study interventions

Investigational medicinal products

• Formulation:

Test drug: Toujeo (insulin glargine 300 U/mL) is supplied as a sterile, non-pyrogenic, clear, colorless solution for SC injection in the Toujeo SoloStar prefilled, disposable pen. Each Toujeo SoloStar contains in total 450 units of insulin glargine (1.5 mL of 300 U/mL insulin glargine solution).

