A relatively homogenous patient population will be selected, reducing potential confounding effects, so that the true differences in the therapeutic effects of Toujeo versus Tresiba can be assessed. The study population includes patients 18-70 years of age with T1DM, on a basal plus mealtime insulin regimen for at least one year, and HbA1c level \geq 7% and <10%. Patients must be on a stable dose of basal/bolus insulin regimen for 30 days before screening.

Repeat assessments of selected PROs will be performed during the study as the exploratory analyses (including patient satisfaction with treatment and patient perception of blood glucose control assessed by Diabetes Treatment Satisfaction Questionnaire [status and change version - DTSQs and DTSQc], MOS Sleep Scale to measure key aspects of sleep and the Work Productivity and Activity Impairment Questionnaire [WPAI]- Diabetes; assessing the impairment on daily work and activities due to diabetes) in order to reveal any potential link between improvement in continues glucose profile and patient well-being.

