8.1.2 Glycated hemoglobin A1c

Glycated hemoglobin A1c is assayed at screening (Visit 1; Week -6/-5), randomization Visit 6 and Visit 18 (Week 12). For the eligibility and efficacy assessments of the study, HbA1c is measured by a certified level I "National Glycohemoglobin Standardization Program", or equivalent certification as per specific country regulations, central laboratory. The screening value will be transferred into the IRT for stratification purpose during the patient randomization at the Visit 6.

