2.1.3.2 Secondary efficacy endpoint(s)

To address the secondary objective of evaluating the glycemic control and variability parameters in each treatment group, efficacy endpoints will be assessed using CGM, HbA1c, and FPG.

At Week 12 the following main secondary endpoints will be assessed using CGM (see Section 2.5.2.1).

- Glucose total coefficient of variation (CV) (%), main secondary endpoint,
- Glucose within-day and between-day CV (%).

Other secondary endpoints to be assessed are:

Based on central lab

- Change from baseline to Week 12 in HbA1c (% and mmol/mol),
- Change from baseline to Week 12 in FPG (mmol/L and mg/dL).

Based on CGM

- Percent time and mean hours per day with glucose <70 mg/dL (on all time [00:00 to 23:59] and during the night [00:00 to 5:59] obtained from CGM,
- Percent time and mean hours per day with glucose >180 mg/dL obtained from CGM.

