2.3.1.2 Per-protocol population

The per-protocol population (PP) is a subset of the ITT population which will comprise all randomized patients, who are exposed, who do not permanently discontinued IMP allocated by IRT, who completed the study as per protocol (as reported in the EOS page) and who do not present any major protocol deviations that potentially impact the primary efficacy results, as presented below:

• Major or critical deviation linked to inclusion criteria:

- From inclusion criterion I02: Patients without T1DM.
- From inclusion criterion I03: Not treated with multiple daily injections (MDI) using basal insulin analog once daily and rapid acting insulin analogs for at least one year
- From inclusion criterion I04: HbA1c <7% or >10%
- Major or critical deviation linked to exclusion criteria:
 - With E09: Patients having received basal insulin dose ≥ 0.6 U/kg body weight within 30 days prior to screening.
 - With E13: Patients who will need real time, flash or implantable CGM for routine care any time during study participation.
 - With E23: Inappropriate CGM use during run-in period evidenced by failure to obtain a minimum of 10 days (not necessarily consecutive) of useable CGM data by the end of run-in.
- Other major or critical deviation potentially impacting primary efficacy results:
 - Not taken only the treatment allocated by IRT (ie, wrong treatment taken at randomization or switch during the study)
 - Wrong stratum of randomization
 - Taken any prohibited medications for more than 10 consecutive days during the study as follows:
 - Any glucose-lowering agents other than IMP, the patient's current background basal insulin analog during the run-in period (which may not be changed during the study), or the patient's existing mealtime insulin (which may not be changed during the study). This includes oral or injectable glucose lowering agents, other type of basal insulin (eg, NPH), pre-mixed insulin, and human regular insulin
 - Insulin pump therapy.
 - Systemic glucocorticoids (topical or inhaled applications are allowed).
 - Patient who did not receive the CGM at Week 9, or for whom there are issues with uploading the CGM data at Week 12. This will be evaluated for patients who completed the treatment period and the study

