2.5.2.3 HbA1c and FPG

HbA1c (mmol/mol) = (HgbA1C% - 2.15) × 10.929

```
FPG (mmol/mol) = FPG mg/dL \times 0.0555
```

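### Inclusion criterion I 04 gives the lower HbA1c limit as 7% and as 48 mmol/mol, but under the SAP's own conversion 7% is 53 mmol/mol and 48 mmol/mol is 6.54%.

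*Protocol*

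**What the plan says.** Protocol section 5.1, criterion I 04, requires "HbA1c \geq 7% (48 mmol/mol) and \leq 10% (86 mmol/mol) at screening". It is the only place in either document that states the entry limits in mmol/mol.

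Elsewhere the limits are in percent only, and the lower one is always 7%:

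- Protocol synopsis (section 1.1), overall design: "having HbA1c \geq 7% and \leq 10% at screening".
- Protocol section 4.2: "HbA1c level \geq 7% and <10" percent. The upper limit is a strict inequality here, which is a separate matter.
- SAP section 2.3.1.2, among the deviations that exclude a patient from the per-protocol population: "From inclusion criterion I04: HbA1c <7% or >10" percent.

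SAP section 2.5.2.3 gives the conversion between units: "HbA1c (mmol/mol) = (HgbA1C% - 2.15) × 10.929". SAP section 2.1.3.2 reports the HbA1c endpoint in both percent and mmol/mol. HbA1c is a central laboratory assay, and Protocol section 8.1.2 adds: "The screening value will be transferred into the IRT for stratification purpose during the patient randomization at the Visit 6". The strata themselves are defined in percent (below 8.0% versus 8.0% or above).

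**The concern.** The bracketed figure should be the same limit in the other unit. At the lower end it is not, so I 04 can be read two ways for a patient whose screening result lies between the two values: eligible by the bracketed figure, ineligible by the percentage.

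This is operative text. Protocol section 5 permits no waivers of the entry criteria, and section 6.3 allows only eligible patients to be randomized. A site that worked from the mmol/mol figure could randomize a patient below 7%. SAP section 2.2.1 counts randomization of an ineligible patient as an irregularity. If the departure from I 04 were rated major or critical, SAP section 2.3.1.2 would remove the patient from the per-protocol population, and so from the first sensitivity analysis of the primary endpoint. The patient would remain in the ITT population. The site would then carry a deviation for following a number printed in the criterion.

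**Working it through.** **Inputs.** Lower pair 7% and 48 mmol/mol, upper pair 10% and 86 mmol/mol (Protocol 5.1, I 04). Conversion (SAP 2.5.2.3): mmol/mol = (% − 2.15) × 10.929. Its inverse: % = mmol/mol ÷ 10.929 + 2.15.

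**Step 1: test the conversion on the upper pair.**
(10 − 2.15) × 10.929 = 85.79, which rounds to the printed 86. The formula reproduces this pair.

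**Step 2: apply it to the lower pair.**
(7 − 2.15) × 10.929 = 53.01 mmol/mol, against 48 printed.
Inverse: 48 ÷ 10.929 + 2.15 = 6.54%.
The gap is 53 − 48 = 5 mmol/mol, or 7.00 − 6.54 = 0.46 percentage points.

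**Step 3: what 48 would correspond to.**
(6.5 − 2.15) × 10.929 = 47.54, which rounds to 48. The printed figure therefore matches a limit of 6.5%, which appears nowhere in the documents.

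**Step 4: the results on which the two readings differ.**
In whole mmol/mol these are 48 to 52. Since 52 ÷ 10.929 + 2.15 = 6.91%, the band is 6.54% to 6.91%. All of it is below 7%, and so falls under the I 04 deviation in the SAP's per-protocol rule.

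**Step 5: how many patients this could touch.**
If eligibility is applied only in percent, none. For a ceiling, suppose the mmol/mol figure were applied everywhere. The documents give no distribution of screening HbA1c, so the following is an assumption: normal, mean 7.8% to 8.3%, SD 0.9 to 1.2 percentage points. With Φ the normal distribution function for that mean and SD, the share below 7% among patients within 48 to 86 mmol/mol (6.542% to 10.019%) is

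[Φ(7) − Φ(6.542)] ÷ [Φ(10.019) − Φ(6.542)].

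| Mean HbA1c | SD 0.9 | SD 1.0 | SD 1.1 | SD 1.2 |
|---|---|---|---|---|
| 7.8% | 11.6% | 12.2% | 12.6% | 12.8% |
| 8.0% | 8.6% | 9.5% | 10.2% | 10.7% |
| 8.3% | 5.2% | 6.3% | 7.2% | 8.0% |

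The range is 5.2% to 12.8%. It is an upper bound on assumed inputs, not an estimate of what happened.

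**Step 6: sample size.**
The plan's formula gives (1.96 + 1.282)² × 1.81 × 14.7² ÷ (0.1 × 56)² = 131.09, against 131 stated. The HbA1c limit does not enter it.

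**The case against.** The strongest reply is that I 04 sets one limit, 7%, followed by a faulty conversion in brackets. If both figures had to be met, anyone at 7% or above would also meet 48 mmol/mol, and the criterion would reduce to 7%. A patient in the 48 to 52 band enters only if a site disregards the printed percentage.

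Several facts also suggest that percent governs in practice. The central laboratory value goes to the IRT for strata defined in percent. The SAP derives mmol/mol from percent. Every other statement of the limit is in percent. The SAP, dated about two years after the protocol, restates I 04 as a deviation in percent alone, so the rule for the analysis sets is settled. On this view the effect may be nil, the ceiling lends weight to a remote case, and the matter is editorial.

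Much of this stands. The likely number of affected patients is small and may be zero, the ceiling rests on assumed inputs, and no analysis rule needs to change. What does not follow is that the text may be left alone. The documents do not say which unit the laboratory report or the eligibility checks use, and the figure sits in an entry criterion that sites apply rather than in background text.

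**Conclusion.** The inconsistency is real and follows from the documents alone. The lower limit in mmol/mol is printed 5 mmol/mol (0.46 percentage points) below the equivalent of 7%; nothing in the protocol or SAP corrects it, and the agreement of the upper pair rules out rounding. Because the lower limit is 7% everywhere else, 48 is the figure out of line.

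The arithmetic is certain and the practical effect is not. No patient is affected if percent governs. The 5.2% to 12.8% ceiling applies only if the mmol/mol figure was used throughout and the assumed HbA1c distribution holds. The consequence is confined to eligibility and to possible exclusions from the per-protocol sensitivity analysis; no bias between arms and no effect on the primary comparison is claimed. It should be corrected, because it concerns an entry threshold and the remedy is small.

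**What to change.** Reconcile the two figures in I 04 by printing 53 mmol/mol in place of 48. This expresses in the second unit the 7% limit that the synopsis, Protocol section 4.2 and the SAP's per-protocol rule already use, and introduces no new threshold.

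Then confirm the limit and the unit set in the central laboratory, IRT and eCRF eligibility checks. The documents do not say whether enrolment has closed. If it has, the useful step is to look for any randomized patient with a screening HbA1c below 7%.

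The analysis sets can stay as they are, since the per-protocol rule already covers anyone admitted below the limit. The cost is one figure in a protocol clarification or the next amendment, plus one check of the eligibility flags. An amendment needs IRB/IEC approval before it is implemented (Protocol section 10.1.1), so it makes sense to combine this correction with other changes.

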5.2 EXCLUSION CRITERIA

Participants are excluded from the study if any of the following criteria apply:

Medical conditions

- E 01. Any clinically significant abnormality identified either in medical history or during screening evaluation (eg, physical examination, laboratory tests, ECG, vital signs), or any AE during screening period which, in the judgment of the investigator, would preclude safe completion of the study or constrains efficacy assessment.
- E 02. End stage renal disease defined as estimated glomerular filtration rate (GFR) modification of diet in renal disease (MDRD) <15 mL/min/1.73 m² or on renal replacement treatment.
- E 03. Laboratory findings at screening:
 - ALT or AST >3 x ULN or total bilirubin >1.5 x ULN (except in case of documented Gilbert's syndrome).
 - Fasting C-peptide >0.2 nmol/L.
- E 04. Retinopathy or maculopathy with one of the following treatments, either recent (within 3 months prior to screening) or planned: intravitreal injections or laser or vitrectomy surgery.
- E 05. Body weight change \geq 5 kg within 3 months prior to screening

Prior/concomitant therapy

- E 06. Participants not on stable dose of basal insulin analog (±20% total daily dose) for at least 30 days prior to screening.
- E 07. Participants having received Toujeo or Tresiba as basal insulin within 30 days prior to screening.
- E 08. Participants not using the same insulins (both basal and rapid) within 30 days prior to screening.
- E 09. Participants having received basal insulin dose ≥0.6 U/kg body weight within 30 days prior to screening.
- E 10. Participants having received any glucose lowering drugs (including any premixed insulins, human regular insulin as mealtime insulins, any others injectable or oral), other than basal and rapid insulin analogs, within 3 months prior to screening.
- E 11. Participants having received glucocorticoids (excluding topical application or inhaled form) for more than 10 days within 3 months prior to screening.
- E 12. Participants having used insulin pump within 6 months prior to screening.

E 13. Participants who will need real time, flash or implantable CGM for routine care any time during study participation.

Prior/concurrent clinical study experience

E 14. Exposure to any investigational drug in the last 4 weeks or 5 half-lives, whichever is longer, prior to screening or concomitant enrollment in any other clinical study involving an investigational study treatment.

Diagnostic assessments

Not applicable.

Other exclusions

- E 15. Any contraindication to use of Toujeo, Tresiba and rapid insulin analogs according to the national product label.
- E 16. Sensitivity to any of the study interventions, or components thereof, or drug or other allergy that, in the opinion of the Investigator, contraindicates participation in the study.
- E 17. Night shift workers.
- E 18. Individuals accommodated in an institution because of regulatory or legal order; prisoners or subjects who are legally institutionalized.
- E 19. Participants dependent on the Sponsor or Investigator (in conjunction with section 1.61 of the ICH-GCP Ordinance E6).
- E 20. Participants are employees of the clinical study site or other individuals directly involved in the conduct of the study, or immediate family members of such individuals.

Additional criteria at the end of the run-in period

- E 21. Participants unwilling or unable to comply with study procedures as outlined in the protocol.
- E 22. Participants who withdraw consent during the screening (starting from signed ICF).
- E 23. Inappropriate CGM use during run-in period evidenced by failure to obtain a minimum of (10 days, not necessarily consecutive) of useable CGM data by the end of run-in (see Section 8.1.1.2 for the definition of useable CGM data).

5.3 LIFESTYLE CONSIDERATIONS

Lifestyle and diet therapy provided before the time of screening is to be continued during the study. Dietary and lifestyle counseling will be given by a healthcare professional and compliance will be checked as per SoA (Section 1.3) and should be consistent with international or local guidelines for patients with T1DM (with regard to the distribution of calories among carbohydrates, proteins, and fats, exercise, etc).

5.4 SCREEN FAILURES

Screen failures are defined as participants who consent to participate in the clinical study but are not subsequently randomly assigned to study intervention. A minimal set of screen failure information is required to ensure transparent reporting of screen failure participants to meet the Consolidated Standards of Reporting Trials (CONSORT) publishing requirements and to respond to queries from regulatory authorities. Minimal information includes demography, screen failure details, eligibility criteria, and any serious adverse event (SAE).

Individuals who do not meet the criteria for participation in this study (screen failure) may be rescreened in cases where original screen failure was due to reasons expected to change at rescreening and based upon the Investigator's clinical judgment. Rescreened patients will be subject to the screening visit procedures/assessments (see following paragraphs) including new informed consent signed and allocation of a new patient number.

6 STUDY INTERVENTION

Study intervention is defined as any investigational intervention(s), marketed product(s), placebo, or medical device(s) intended to be administered to a study participant according to the study protocol.

6.1 STUDY INTERVENTION(S) ADMINISTERED

Table 2 - Overview of study interventions administered

Study intervention name	Toujeo	Tresiba
Dosage formulation	Toujeo (insulin glargine 300 U/mL) is supplied as a sterile, non-pyrogenic, clear, colorless solution for SC injection in the Toujeo SoloStar prefilled, disposable pen.	Tresiba (insulin degludec 100 U/mL) is supplied as a sterile, non-pyrogenic, clear, colorless solution for SC injection in the marketed Tresiba FlexTouch prefilled, disposable pen.
Unit dose strength(s)/Dosage level(s)	Each Toujeo SoloStar contains in total 450 units of insulin glargine (1.5 mL of 300 U/mL insulin glargine solution). Mixing of Toujeo with other insulin products or dilution is not allowed	Each Tresiba FlexTouch contains in total 300 units of insulin degludec (3 mL of 100 U/mL insulin degludec solution). Mixing of Tresiba with other insulin products or dilution is not allowed.
Route of administration	SC self-injection	SC self-injection
Dosing instructions	Toujeo will be self-administered by SC injection once daily in the morning ^a , which is defined as the time period between waking up and prebreakfast. The clock time for the morning injection (hh:mm) will be established at the discretion of the patient/Investigator at the time of randomization and will be maintained for the duration of the study.	Tresiba will be self-administered by SC injection once daily in the morning ^a , which is defined as the time period between waking up and prebreakfast. The clock time for the morning injection (hh:mm) will be established at the discretion of the patient/Investigator at the time of randomization and will be maintained for the duration of the study.
	Injection site should be alternated between the left and right anterolateral and left and right posterolateral abdominal wall or thighs or upper arms ^b .	Injection site should be alternated between the left and right anterolateral and left and right posterolateral abdominal wall or thighs or upper arms ^b .
Packaging and labeling	Toujeo SoloStar pens will be supplied as open label treatment kits containing 5 Toujeo SoloStar pens. Each SoloStar pen will be labeled as required per country requirement. Treatment labels will indicate the treatment number used for treatment allocation. The Investigator's name, the patient number and visit number will be entered manually by the site staff on the treatment box label prior to dispensing.	Tresiba FlexTouch pens will be supplied as open label treatment kits containing 5 Tresiba FlexTouch pens. Each FlexTouch pen will be labeled as required per country requirement. Treatment labels will indicate the treatment number used for treatment allocation. The Investigator's name, the patient number and visit number will be entered manually by the site staff on the treatment box label prior to dispensing.

a Patients taking their current basal insulin at any time (eg, evening) other than in the morning should switch their injection time to the morning at randomization. The instruction on changing injection time should be given by the Investigator in accordance with the National Product Label of the patient's current basal insulin. On the day of switching injection time, the total dose of current basal insulin and the pre breakfast (if applicable) rapid action insulin may need to be reduced based on the physician's medical judgment. For example, on the day before changing injection time, the dose of the current basal insulin may be changed to approximately 1/2 to 2/3 of the total daily dose, which would

then be injected in the evening as the patient's usual injection time. On the following day, the dose of randomly assigned basal insulin (IMP) will be equal to the total daily current basal insulin dose and injected in the morning before breakfast.

b Within a given area, location should be changed (rotated) at each time to prevent injection site skin reactions. The injection sites for IMP and noninvestigational medicinal product (NIMP) should be different so that, if any, an injection site reaction can be attributed specifically either to IMP (Toujeo or Tresiba) or NIMP (mealtime insulin).

INVESTIGATIONAL MEDICINAL PRODUCT(S)

An instruction leaflet, which explains how to use the disposable pen and needles, will be provided for Toujeo and Tresiba. All patients will be trained by study staff at Visit 6 (randomization) on how to use the pen correctly, how to rotate injection site to avoid skin reactions, how to store the pen and how to change the needle. Training will be repeated as often as deemed necessary by study site staff during the treatment period. For the duration of the treatment, patients will be required to use the same type of study drug disposable pens and needles. Each patient will be supplied with the appropriate number of pens according to the dispensing scheme indicated in the SoA (see Section 1.2).

Toujeo (insulin glargine 300 U/mL)

Toujeo will be self-administered with the prefilled, disposable Toujeo SoloStar pen specifically labeled for use in the study. This pen allows dose setting in the range of 1–80 units with minimum of 1 unit increment. The dose of Toujeo is titrated according to the patient's need for insulin glargine.

The following pen needles will be provided for use with the disposable injection pen devices:

- BD Ultra Fine Needles 31 G x 5 mm.
- BD Ultra Fine Needles 31 G x 8 mm.

Tresiba (insulin degludec 100 U/mL)

Tresiba will be self-administered with the prefilled, disposable Tresiba FlexTouch pen specifically labeled for use in this study. This pen allows dose setting in the range of 1–80 units with minimum of 1 unit increment. The dose of Tresiba is titrated according to the patient's need for insulin degludec

The following pen needles will be provided for use with the disposable injection pen devices:

- BD Ultra Fine Needles 31 G x 5 mm.
- BD Ultra Fine Needles 31 G x 8 mm.

NONINVESTIGATIONAL MEDICINAL PRODUCT(S)

The protocol-mandated background therapy is mealtime insulin analog, ie, rapid insulin analogs (eg, insulin glulisine, insulin lispro or insulin aspart). Patients in both treatment groups will continue with their short-acting mealtime insulin analogue which has been used for at least 30 days before the screening visit and which will be continued throughout the study. The cost of the mealtime insulin analogue may be reimbursed if not covered by health insurance and if allowed by local regulations. Alternatively, the sponsor provided insulin glulisine may be offered.

Dose adjustment of mealtime insulin can be based on a pattern of post-meal SMPG data from the prior 3 days (simple titration) OR the carbohydrate content of the meal. The injection sites should be different from the IMP (Toujeo or Tresiba) for the fast-acting mealtime insulin analogs so that any injection site reactions can be attributed specifically either to the fast-acting insulin or to the IMP. Changes in the body areas used for injection of basal (current during run-in or IMP during the randomized treatment period) and mealtime insulin should be avoided as far as possible during the study.

